12 ANALYTICAL PLAN

12.1 Sample Size

As the study is not designed to compare the efficacy of the two treatments, there is no formal sample size calculation.

12.2 Analytical Populations

mITT Population: The mITT population includes all subjects who received any administration of an investigational product.

Evaluable Population: The evaluable population will include all subjects who received daily doses of investigational product for at least 25 of the total of 28 days, had lesion measurements at the Month 7 for CL or the month 13 visit for ML, and who did not receive rescue medications to treat leishmaniasis at any time during the study.

Efficacy outcomes will be presented separately for subjects with CL and ML.

Safety Population: The safety population includes all subjects who received any administration of investigational product.

12.3 General Analytical Procedures

Descriptive statistics will be used to present study data. Continuous variables will be presented as number of observations (n), mean, standard deviation (SD), median, minimum and maximum values. Categorical variables will be presented as counts and percentages.

12.4 Analysis of Baseline Data

By-subject and summaries of the baseline data will be provided for the mITT, and evaluable populations.

12.5 Analysis of Treatment Compliance Data

By subject and summaries of compliance with scheduled treatments will be provided, including total exposure (number of days and total dose) to investigational product.

12.6 Analysis of Efficacy Outcomes of CL Subjects

12.6.1 Lesion Area Measurements

Summary statistics for each subject will include lesion area and change from baseline at each measurement time point.

12.6.2 Lesion and Subject Cure Rate

For each subject, the proportion of lesions at each measurement time point that have healed, improved, did not change, worsened, or relapsed will be calculated. Also for each subject, the proportion of all lesions that cured and all lesions that failed will be presented. The proportion of subjects who cure or fail will be calculated. This data will be presented for the mITT and evaluable populations.

12.6.3 Handling of Missing Data

Missing lesion measurements will be ignored when presented as summary statistics of lesion areas and lesion responses as presented by numbers of lesions evaluated at each time point. Subjects who do not provide lesion response measurements at their final scheduled follow up will be considered lesion ane subject failures in the mITT analysis.

Note that if a subject does not appear at the scheduled Study Week 6, Month 3, or Month 7 visits, the subject's estimate of his/her lesion response may be obtained from the subject by telephone, and will be noted as obtained in that manner. Such data is not defined as missing. For such data, the Treating Physician and the PI will jointly decide if the subject's estimate is likely to be reliable. In a single-group non-comparative study such as this one, errors in interpretation will only apply to miltefosine subjects and will not be corrected by being equally applied to a comparator group. Therefore, it is important for subject, physician, and Investigator to avoid two potential errors: 1) erroneously viewing a lesion as healed when in fact it is still present, 2) erroneously viewing a lesion as failed because a subject does not show up for clinic, when in fact the lesion has healed and the subject does not want to spend time coming to clinic.

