10.1.3 Definition of Clinical Responses

Lesion Cure: Lesion is healed at the Month 7 visit.

Lesion Failure: Each lesion will be considered a failure if it does not meet the criteria for cure (missing data will be considered failures). The intended response to therapy is a progressive diminution in lesion size and no relapse. Lesion failure therefore is defined as clinically worse at the end of therapy or thereafter, OR does not improve at the Week 6 or Month 3 visit, OR is not healed at the Month 7 visit, OR relapses.

NOTE: Parasitological responses can assist the clinician in evaluating the clinical response of the lesion. If the Treating Physician has parasitologically re-investigated a slowly responding lesion

at time-points greater than 2 weeks after the end of therapy, and parasites are still present by microscopy or culture, the physician may interpret the data as indicating therapeutic failure. Note that the presence of parasites prior to 2 weeks after the end of therapy should not be interpreted. Note that because PCR is more sensitive than microscopy or culture on which the clinical experience in the literature is based, PCR positivity post therapy cannot easily be interpreted.

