10.3 Withdrawal from Protocol for Lack of Efficacy

The Treating Physician may choose to withdraw the subject from the protocol for lack of efficacy and to initiate rescue (alternative) therapy for ML or CL.

For CL, the basis for lack of efficacy will generally be failure of at least one lesion: lesion has worsened at the end of therapy or thereafter, OR does not Improve at the Week 6 or Month 3 visit, OR is not healed at the Month 7 visit, OR relapses, or a new lesion.

For ML, the basis for lack of efficacy will generally be failure: clinically worse (by MSS score) at the Week 6 visit of or thereafter, OR does not improve at the Month 3 or Month 6 visit, OR is not healed at the Month 13 visit, OR relapses.

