12.7.3 Handling of Missing Data

Missing lesion measurements will be ignored when presented as summary statistics of lesion areas and lesion responses as presented by numbers of lesions evaluated at each time point. Subjects who do not provide lesion measurements at their final scheduled follow up will be considered clinical failures in the mITT analysis.

Note that because the subject cannot accurately examine his/her oro-nasal membranes, subject reports of physical mucosal examination cannot be accepted.

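### By-visit response proportions can be biased upward, because failing subjects may leave for rescue and then drop out of the denominator

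*Combined protocol and SAP*

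**What the plan says.** **Outputs.** For each CL subject, section 12.6.2 asks that "the proportion of lesions at each measurement time point that have healed, improved, did not change, worsened, or relapsed will be calculated". It also asks for lesion and subject cure and failure proportions, and adds: "This data will be presented for the mITT and evaluable populations". For ML, section 12.7.2 asks for the share of subjects in each response category at every visit.

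**Missing data in those outputs.** For CL, section 12.6.3 states: "Missing lesion measurements will be ignored when presented as summary statistics of lesion areas and lesion responses". The same sentence ties these summaries to the count of lesions assessed at a given visit. For ML, section 12.7.3 opens in the same way: "Missing lesion measurements will be ignored when presented as summary statistics".

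**Missing data in the cure rate.** Both sections then apply a different rule to the mITT analysis: a subject with no measurement at the last scheduled visit is a failure. Section 10.1.3 does the same when it classifies lesions as cured or failed: "missing data will be considered failures".

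**Ways to leave.** Section 10.3 provides: "The Treating Physician may choose to withdraw the subject from the protocol for lack of efficacy", and for starting other therapy. One of its CL grounds reads "OR does not Improve at the Week 6 or Month 3 visit"; others are worsening from the end of therapy onward, relapse and a new lesion. Section 8.8 bars other antileishmanial drugs while a subject is on protocol, so a rescued subject has to leave. Section 8.6 asks that a subject who withdraws during follow-up be contacted, where possible, for a lesion measurement. It schedules nothing after that.

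**Telephone reports.** Under 12.6.3, a CL subject's own report by telephone does not count as missing, provided the Treating Physician and PI judge it reliable. Under 12.7.3, self-reports of mucosal findings are not accepted.

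**The concern.** Dropping missing values from a descriptive table does little harm when missingness is unrelated to outcome. Here one route to missingness is the outcome itself: a subject who is not responding may be withdrawn, rescued and not measured again under the protocol. From the next visit on, that subject's unhealed lesions are absent from the denominator while healed lesions remain. The proportion healed can then rise between visits without any lesion having healed.

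The study has a single group, so no control arm shows how much of a rise is artefact. Section 12.6.3 itself warns that errors of interpretation in this design are not balanced by a comparator. At Month 7 the report could also carry two healed figures for the same mITT population, one from the by-visit table and one from the cure analysis, with nothing to explain the gap.

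**Working it through.** The plan gives no sample size calculation and no expected by-visit rate, so there is no design figure to reproduce. The size is illustrated with outcome mixes that the protocol cites.

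**Inputs**
- Guatemala, miltefosine arm (4.2.8.2, Table 1): 20 cured, 18 failed, 2 unassessable, 40 treated.
- Bolivia, miltefosine arm (4.2.8.3, Table 3, six months): 36 healed, 5 failed, 3 lost, 44 treated.
- ML cohort (4.2.8.5): 51 cured by that study's definition, 72 evaluable, 78 treated; hence 72 − 51 = 21 failed and 78 − 72 = 6 not evaluable.
- w, the share of failures withdrawn and unmeasured at the final visit. The documents do not give it. Assumption: 0% to 100%.
- Simplification: one lesion per subject.

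**Check of the cited rates.** 20/40 = 50%, 20/38 = 53% and 36/41 = 88% agree with the protocol's tables.

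**Formulas**
- Under the ignore-missing rule: healed / [healed + failed × (1 − w)], lost subjects also dropped.
- Comparator: healed / all treated.

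**Results**

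| Mix | w = 0% | w = 50% | w = 100% | All treated |
|---|---|---|---|---|
| Guatemala | 20/38 = 52.6% | 20/29 = 69.0% | 20/20 = 100% | 20/40 = 50.0% |
| Bolivia | 36/41 = 87.8% | 36/38.5 = 93.5% | 36/36 = 100% | 36/44 = 81.8% |
| ML cohort | 51/72 = 70.8% | 51/61.5 = 82.9% | 51/51 = 100% | 51/78 = 65.4% |

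The gap at w = 0 comes from losses alone (Guatemala: 52.6 − 50.0 = 2.6 points). Withdrawing half of the failures adds about 16 points in the Guatemala mix (52.6% to 69.0%) and about 6 in the Bolivia mix (87.8% to 93.5%).

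**The artefact in isolation (assumed numbers).** Take 20 one-lesion subjects, 10 of them healed from Week 6 and none healing later. Three failures are withdrawn after Week 6 and three after Month 3. The table reads 10/20 = 50.0% at Week 6, 10/17 = 58.8% at Month 3 and 10/14 = 71.4% at Month 7, with no further healing.

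**The case against.** Several points on the other side are sound.

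- **Withdrawal is discretionary.** Section 10.3 permits it and does not require it. The visit that reveals a failure is itself measured, and a lesion that fails only by being unhealed at Month 7 is by definition seen there. A reader might infer that failing subjects will be withdrawn and that the last row will show 100% healed. The documents do not support that; 100% is the upper bound. In the Bolivian study 4 failures were recorded at the assessment before the last and 5 at the last, so even withdrawing all 4 early would give 36/37 = 97.3%.
- **The mITT cure rate is protected.** A reader might infer that this endpoint is inflated. It is not, because missing counts as failure there.
- **Section 10.1.3 is not contradicted.** Its missing-equals-failure rule governs the cure or failure classification; the ignore-missing rule governs descriptive response categories. They are different outputs, although they meet at Month 7.
- **Other outputs show the time course.** Lesion area (12.6.1) and MSS (12.7.1) are also summarised by visit, so the response tables are not the only description. Lesion area falls under the same ignore-missing rule.
- **Healing is real.** In the Bolivian study the healed share was 34% at end of treatment, 70% at one month and 91% at the next assessment. A rise over visits is not in itself evidence of artefact.
- **The CL proportions are worded per subject.** One subject's withdrawal cannot alter another's within-subject proportion. Pooling is explicit only for ML; for CL it is inferred from the lesion counts in 12.6.3. But a withdrawn subject has no evaluated lesions, so any summary across subjects still omits that subject.
- **Healed subjects may also stay away.** That pulls the other way, and 12.6.3 warns against treating them as failures. Telephone reports limit this for CL but not for ML. It is a reason to show other missing data separately rather than as not healed.

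These points limit the size and reach of the problem. They do not supply a rule that keeps withdrawn failures in later tables.

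**Conclusion.** The concern holds for by-visit response proportions pooled across subjects: clearly for ML, by implication for CL. The direction of the bias from withdrawal for lack of efficacy is upward; its size is unknown, because the share of failures withdrawn is not given. If half were withdrawn, the Guatemala mix would read 69.0% against 50.0% of all treated, and the Bolivia mix 93.5% against 81.8%; if none were, the remaining excess would come from losses alone (52.6% and 87.8%). These figures assume one lesion per subject, outcome mixes like those cited, and no later measurement of withdrawn failures.

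No hypothesis test depends on these tables and the final mITT cure rate stands, so this is an inexpensive improvement to description. The evaluable population excludes rescued subjects by definition (12.2). That is a separate matter, which this change does not address, and the evaluable tables cannot serve as a check on the mITT ones.

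**What to change.** Amend 12.6.3 and 12.7.3 for the mITT by-visit response categories:

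1. Use all mITT lesions (CL) or all mITT subjects (ML) as the denominator at every visit.
2. After withdrawal for lack of efficacy, or rescue, carry the failure forward to every later visit.
3. Show other missing data as a separate row, not as not healed. Count CL telephone reports judged reliable as observed.
4. Keep observed-case summaries, with n at each visit, for lesion area and MSS.

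Whatever the share withdrawn, the Guatemala mix would then read 20/40 = 50.0% healed, 18/40 = 45.0% failed and 2/40 = 5.0% missing. The Bolivia mix would read 36/44 = 81.8%, 5/44 = 11.4% and 3/44 = 6.8%. The Month 7 healed row would rest on the same denominator as the mITT cure analysis.

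The change uses data already collected and alters no visit or clinical rule. Section 14 leaves a separate statistical analysis plan to be prepared, where the table shells can be set. The cost is slightly more table work and less favourable by-visit proportions.

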12.7 Analysis of Efficacy Outcomes of ML Subjects

12.7.1 Lesion assessments

Summary statistics for each subject will include the individual components of the MSS score and the total MSS score, and change from baseline in both parameters, at each measurement time point.

12.7.2 Subject Cure Rate

The proportion of subjects at each measurement time point with clinical cure, improvement, fail, and relapse will be calculated. Data will be presented for the mITT and evaluable populations.

12.7.3 Handling of Missing Data

Missing lesion measurements will be ignored when presented as summary statistics of lesion areas and lesion responses as presented by numbers of lesions evaluated at each time point. Subjects who do not provide lesion measurements at their final scheduled follow up will be considered clinical failures in the mITT analysis.

Note that because the subject cannot accurately examine his/her oro-nasal membranes, subject reports of physical mucosal examination cannot be accepted.

12.8 Analysis of Safety Data

Symptoms (subjective AEs) will be coded using the most recent version of the Medical Dictionary of Regulatory Affairs (MedDRA) by assigning a preferred term and will be grouped by system, organ, and class (SOC) designation. Listings of each individual AE including start date, stop date, severity, relationship, duration, and outcome will be provided.

Laboratory data and physical signs (including vital signs) will be presented as summary statistics by Study Day including changes from baseline as well as in by-subject data listings. A summary and listing of analyte concentrations and vital signs for subjects with levels outside normal laboratory limits will also be presented. Clinically significant AEs, SAEs, discontinuation due to AEs, and other significant AEs will be individually listed and narrated.

The above safety analysis will be provided for the mITT and Evaluable populations.

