4.2.3 Warnings and Precautions

Impavido is contraindicated in pregnancy. Women of childbearing potential have to use effective contraception during and up to 3-6 months after treatment. Vomiting/diarrhea are very common/common side effects of therapy with Impavido and can compromise the efficacy of oral contraception. The subject must be informed by her physician of these symptoms and if necessary, suitable alternative methods of contraception must be used.

Subjects with ALT (liver function), serum creatinine, and blood urea nitrogen (BUN) (renal function) 1.25 times above the normal range were generally excluded from the clinical studies. Thus, data from subjects with abnormalities of liver and kidney function are not available.

Treatment with Impavido may lead to an increase in serum creatinine. Kidney function must be evaluated in biweekly intervals. In subjects with clinically significant abnormality in kidney function, monitoring should be continued until normalization.

Gastrointestinal symptoms such as nausea, vomiting, diarrhea, and a feeling of motion sickness are possible side effects of therapy with Impavido. The subjects must be instructed that in case of prolonged persistence of vomiting and diarrhea a sufficient fluid intake must be ensured, to avoid dehydration and consequently the risk of an impaired renal function.

Organ system	Very Common	Common	
	>10% of subjects	1-10% of pts	
Gastrointestinal	Nausea	Motion sickness	
	Vomiting Grade 1-2*	Diarrhea Grade 1*	
	ç	Headache	
Renal	Creatinine elevation		
	Grade 1*		

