9.3 Assessment During Miltefosine Treatment

9.3.1 Study Day 1

Study Day 1 visit is conducted on the first day of miltefosine therapy and includes:

- 1. Medical History record changes in medical history or medications since screening visit
- 2. Physical Examination form perform brief physical exam including vital signs
- 3. Pregnancy test form perform a pregnancy test in women of child bearing potential, unless the screening pregnancy test was performed within the previous 24 hours.
- 4. Complete the eligibility checklist to ascertain if the subject still meets all of the eligibility criteria, then the subject will receive the first dose of medicine.
- 5. Record any AEs

9.3.2 Study Days 7 and 14

Two visits are scheduled to occur between Study Day 2 through Study Day 27 and should preferably occur at the end of Study Week 1 and Study Week 2 with in a three-day window either side of Day 7 and Day 14. At these two visits the following assessments are performed:

- 1. Medical History The subject will return to clinic for evaluation; record any AEs
- 2. Treatment form complete log
- 3. If more medication than that which was dispensed on day 1 is needed, further medication will be dispensed on the nominal day 14 visit
- 4. Chemistry record values of ALT and creatinine in the serum (Day 14 visit only)
- 5. Record any AEs

9.3.3 Study Day 28

Study Day 28 visit is conducted the last day of miltefosine therapy and includes:

- 1. Medical History record changes in medical history or medications
- 2. Physical examination record vital signs
- 3. Interval History of leishmaniasis:
 - a. CL lesion reactions
 - b. ML evolution of symptoms
- 4. CL subjects: Re-examination of each CL lesion and re-recording the size of the lesion ulceration (length/width), other notable characteristics of the lesion

- 5. ML subjects: Re-examination of mucosal membranes
- 6. Pregnancy test in women of child-bearing potential
- 7. Chemistry record values of ALT and creatinine in the serum
- 8. Record any AEs

9.3.4 Study Week 6

Two weeks after the Study Day 28 visit record the following:

- 1. Medical History record changes in medical history or medications since 28-day visit
- 2. Physical examination perform brief physical exam if appropriate, and vital signs
- 3. Interval History of leishmaniasis since last visit to include:
 - a. ML re-examination of mucosal membranes. Evolution of symptoms

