 - b. CL subjects re-examination of each CL lesion and record the size of the lesion ulceration (length/width), other notable characteristics of the lesion
- 4. ALT and creatinine: Repeat if abnormal on last examination
- 5. Record any AEs

9.3.5 Study Month 3

Study Month 3 visit is conducted 2 months after the end of miltefosine therapy and includes:

- 1. Medical History record changes in medical history or medications since 6-week visit
- 2. Physical Examination perform brief physical exam if appropriate, and vital signs
- 3. Interval History of leishmaniasis since last visit to include:
 - a. ML re-examination of mucosal membranes. Evolution of symptoms.
 - b. CL subjects re-examination of each CL lesion and record the size of the lesion ulceration (length/width), other notable characteristics of the lesion
- 4. Pregnancy test in women of child bearing potential
- 5. ALT and creatinine: Repeat if abnormal on last examination
- 6. Record any AEs

9.3.6 Study Month 7

Study Month 7 visit is conducted 6 months after the end of miltefosine therapy. Final follow up visit for CL subjects and includes:

- 1. Medical History record changes in medical history or medications since 3-month visit
- 2. Physical Examination perform brief physical exam if appropriate, and vital signs
- 3. Interval History of leishmaniasis since last visit to include:
 - a. ML re-examination of mucosal membranes. Evolution of symptoms
 - b. CL subjects re-examination of each CL lesion and record the size of the lesion ulceration (length/width), other notable characteristics of the lesion
- 4. Pregnancy test in women of child bearing potential
- 5. ALT and creatinine: Repeat if abnormal on last examination
- 6. Record any AEs

9.3.7 Study Month 13

Study Month 13 visit is conducted 12 months after the end of miltefosine therapy. Final follow up visit for ML subjects and includes:

- 1. Medical History record changes in medical history or medications since 7-month visit
- 2. Physical Examination perform brief physical exam if appropriate, and vital signs

- 3. Interval History of leishmaniasis since last visit to include:
 - a. ML re-examination of mucosal membranes. Evolution of symptoms.
 - b. CL subjects re-examination of each CL lesion and record the size of the lesion ulceration (length/width), other notable characteristics of the lesion
- 4. ALT and creatinine: Repeat if abnormal on last examination
- 5. Record any AEs

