11.1.3 Laboratory Assessments

Venous blood will be collected during screening for measurement of hematology parameters to be reported [white blood cells (WBC), neutrophil count, hemoglobin, hematocrit, and platelet count] and chemistry parameters including glucose, sodium, potassium, creatinine, ALT, and bilirubin. These baseline values will be used to determine if the subject has a concomitant medical condition.

On nominal days 14 and 28, a blood sample will be collected for AST and creatinine only. On follow up visits at Month 3, Month 7, and Month 13, blood will again be collected for ALT and creatinine if on the previous sample the ALT value was above the upper limit of normal, or if the creatinine clearance was abnormal. Serum creatinine levels will be used to calculate creatinine clearance (CrCl) according to the Cockroft-Gault formula as follows:

Males	CrCl (mL/min) = [140 - age (years) x body weight (kg)] (72) x (serum creatinine [mg/dL])		
Females	$CrCl (mL/min) = 0.85 \times [140 - age (years) \times body weight (kg)]$		

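### By-visit ALT and creatinine means after Day 28 come from subjects selected for abnormal values and are not comparable with Day 28

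*Combined protocol and SAP*

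**What the plan says.** **Sampling.** The schedule (Sections 2 and 9) and Section 9.3 set ALT and creatinine for every subject at screening, on nominal Day 14 and on Day 28; the treatment-visit instruction is "Chemistry record values of ALT and creatinine in the serum". From Week 6 it becomes "ALT and creatinine: Repeat if abnormal on last examination", repeated at Months 3, 7 and 13 and matched by footnote g of the schedule.

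**Analysis.** Section 12.8 says that laboratory data "will be presented as summary statistics by Study Day including changes from baseline". It has no rule for visits at which only abnormal subjects are sampled, and the missing-data rules in 12.6.3 and 12.7.3 deal with lesions only. Section 12.3 fixes the statistics: "Continuous variables will be presented as number of observations (n), mean, standard deviation (SD), median, minimum and maximum values". Section 12.8 also plans by-subject listings, and adds: "A summary and listing of analyte concentrations and vital signs for subjects with levels outside normal laboratory limits will also be presented".

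**A second version of the sampling rule.** Section 11.1.3 says "On follow up visits at Month 3, Month 7, and Month 13, blood will again be collected for ALT and creatinine" and gives the condition as "if on the previous sample the ALT value was above the upper limit of normal, or if the creatinine clearance was abnormal". It does not list Week 6, it uses creatinine clearance rather than serum creatinine, and it names AST rather than ALT for Days 14 and 28.

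**The concern.** The Day 28 column describes the whole cohort. The Week 6 column describes those whose Day 28 value was abnormal, and each later visit selects again from those still abnormal. Read along the row, such a table mixes change over time with change in who is measured.

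Tolerance is the secondary objective, and raised creatinine is a laboratory toxicity that the protocol expects: 29 of 89 on miltefosine against 4 of 44 on placebo (Table 2 in 4.2.8.2). The clinical summary in 4.2.8.6 calls these elevations reversible, and Section 4.2.3 asks for follow-up of recovery: "In subjects with clinically significant abnormality in kidney function, monitoring should be continued until normalization". The follow-up draws exist to show recovery, yet no planned table counts how many abnormal subjects returned to normal, by when, and how many were never retested.

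**Working it through.** The plan has no figure of its own to reproduce here: no sample size, power or alpha is stated. The background rates check: 29/89 = 32.6% (printed 33), and 28/29 = 96.6% of the elevations were grade 1 (printed 97).

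**Step 1. How many subjects are redrawn.** Enrolment is 10 to 20 a year for 1 to 5 years (7.1.1), so 10 to 100 in total. Assume that 32.6% have abnormal creatinine at Day 28; Table 2 gives no time point, so this is an assumption. Week 6 then rests on about 3 of 10, 7 of 20 or 33 of 100 subjects, and about 67% have no later value.

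**Step 2. Size of the selection.** If Day 28 values are normal and the top p = 0.326 are redrawn, z = 0.451 and their mean lies k = φ(z)/p = 0.360/0.326 = 1.106 SD above the cohort mean.

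**Step 3. Effect on the table.** Assumed inputs in mg/dL, none from the documents: true baseline mean 0.90 (SD 0.13), true rise at Day 28 mean 0.12 (SD s = 0.08 to 0.12), all independent, measurement error SD 0.05. The Day 28 mean is 1.02, with SD S = √(0.13² + s² + 0.05²) = 0.161 for s = 0.08 and 0.184 for s = 0.12. In the redrawn subset:

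- mean baseline = 0.90 + k × 0.13²/S = 1.016 (s = 0.08) or 1.002 (s = 0.12)
- mean rise = 0.12 + k × s²/S = 0.164 or 0.207

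If a fraction f of every rise remains at Week 6, the subset's change from baseline is f × (mean rise), and its level is (mean baseline) + f × (mean rise):

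| f | Change, all | Change, redrawn | Level, all | Level, redrawn |
|---|---|---|---|---|
| 0 | 0.00 | 0.00 | 0.90 | 1.00–1.02 |
| 0.25 | 0.03 | 0.04–0.05 | 0.93 | 1.05–1.06 |
| 0.50 | 0.06 | 0.08–0.10 | 0.96 | about 1.10 |
| 0.75 | 0.09 | 0.12–0.16 | 0.99 | 1.14–1.16 |

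The Day 28 values for comparison are a change of 0.12 and a level of 1.02, both in all subjects.

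**Step 4. When the change column misleads on direction.** It matches or exceeds Day 28 when f ≥ 0.12/(mean rise in the subset): 0.12/0.164 = 0.73, or 0.12/0.207 = 0.58. Hence about 60 to 75%.

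**Step 5. Other assumptions.** A separate simulation in units of the upper limit of normal assumed a baseline mean of 0.75 to 0.78, a mean rise of 0.14 to 0.17 and 31 to 33% abnormal at Day 28. The redrawn subset's mean change was about 1.4 to 2.1 times the all-subject value whenever part of the rise remained, and the break-even was about 50 to 70%. If subjects normal at Day 28 had no rise at all, the break-even would fall to about 33%. At Month 7, with the rise fully gone, the subset's mean change was about 0 but its mean level was 0.90 to 1.04 against a baseline of 0.75 to 0.78, and only 0.1 to 6% of subjects were drawn.

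**The case against.** The strongest reply concerns the change-from-baseline column. A subject who recovers contributes one normal value before leaving the sample, so full recovery by Week 6 shows as zero, and half recovery still shows a fall from 0.12 to 0.08–0.10. That stands. A reader might infer that the table must make reversible toxicity look persistent, or that it cannot show reversal at all; the documents and the arithmetic support neither. What remains is that the fall is understated. With half remaining, the redrawn subjects' own fall from Day 28 is 0.10 to 0.12 (1.198 − 1.098 and 1.223 − 1.105), while the table shows 0.02 to 0.04.

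The second reply is that other planned output covers the point: n is printed, subjects are listed, out-of-range values are summarised, and clinically significant abnormalities are recorded as adverse events with an outcome. With 3 to 33 subjects redrawn, a listing can be read by eye. This stands against any claim that recovery could not be traced. It does not correct the means, fix a denominator or give a count of resolutions.

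The third reply is that Study Day could be read literally, since later visits are called Study Week and Study Month, so the summaries would stop at Day 28. That reading is strained, because nothing else in 12.8 limits the summary to those visits. If it is what was meant, one sentence would settle it.

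Fourth, the magnitudes are soft. Under 11.1.3 both analytes are drawn if either trigger is met, so some subjects with normal creatinine would enter and dilute the selection. Clearance also depends on age and weight, so the redrawn set need not be the top third of serum creatinine. This stands as a limit on the size of the effect.

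Finally, the study is single-arm and descriptive, and Section 14 leaves a statistical analysis plan still to be prepared. That lowers the stakes and makes it easy to settle the matter there.

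**Conclusion.** The point holds as one of comparability. Following 12.8 as written places a subset selected for abnormal values beside the full Day 28 cohort. Mean levels in that subset are inflated and can stay at or above the Day 28 mean while values recover. The mean change is overstated relative to all subjects while part of the rise remains (0.08 to 0.10 against 0.06 mg/dL at half remaining). It can look persistent or worse at about 60 to 75% remaining or more, and it is right at full recovery. These sizes rest on assumed baseline, rise and error values and on 32.6% being abnormal at Day 28; the break-even moves to about 50 to 70% under the alternative assumptions. The direction does not depend on the exact values, provided that subjects abnormal at Day 28 had larger rises on average than the cohort. No primary result or decision rule is affected. It should be corrected before tables are programmed, because it bears on the secondary objective and on the recovery of an expected toxicity.

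**What to change.** 1. In 12.8 and the analysis plan, limit by-Study-Day summary statistics and changes from baseline for ALT and creatinine to screening, Day 14 and Day 28.
2. Add one table for Week 6 onward. Over the fixed number abnormal at Day 28, report for each visit the number retested, back to normal, still abnormal and not retested, with the paired change from Day 28 in those retested. Show subjects abnormal at early withdrawal separately; Section 8.6 names only creatinine for that assessment.
3. Footnote that the paired change includes some regression to the mean, because the subjects were chosen on their Day 28 value. Under the inputs above this is k × 0.05²/S, about 0.015 to 0.017 mg/dL. The counts should therefore lead.
4. Reconcile 11.1.3 with the schedule and Section 9.3 on whether Week 6 is included, on AST or ALT at Days 14 and 28, and on serum creatinine or creatinine clearance as the trigger. State also whether one abnormal analyte prompts a redraw of both. These points define who is redrawn, and so the denominator of the new table.

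The cost is a few sentences and one table shell. Items 1 to 3 need no new samples or visits.
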